### **12.5. Reporting Method of Adverse Event**

#### **12.5.1. Reporting of Adverse Event**

The investigator is responsible to make assessment of all adverse events occurring during the clinical study period and to record them in the case report forms. All adverse events are to be analyzed in the clinical study report and will be assessed.

#### **12.5.2. Reporting of Serious Adverse Event · Adverse Medical Device Effect**

Upon the occurrence of any serious adverse event/adverse device effect, the investigator is required to record it in the case report form and the serious adverse event/adverse device effect record form provided by the sponsor, and must report it to the sponsor within 24 hours from the time that the incidence has been known, whether or not related to the investigational device.

The sponsor must notify all unexpected, serious device effects to the investigator, the institutional

review board (IRB) (only applicable when the principal investigator did not report to the IRB or when the reported details require changes) and the Minister of Food and Drug Safety within the time periods specified by each section of the followings.

- 1) Resulted in death or life threatening, the sponsor should report the case within 7 days from the day the fact had been reported or known. However, in such case, the detailed information should be reported additionally within 8 days since the date of initial report.
- 2) In case of all other unexpected serious adverse device effects, the case should be reported within 15 days from the date of report received or getting to know about them.

When there is any additional information regarding the serious adverse events/adverse device effects reported, the sponsor should keep reporting until the adverse device effect is resolved (referring to the disappearance of the adverse device effect or to the impossible follow-up).

#### **12.5.3. Reporting of Device Deficiencies**

All deficiencies of a medical device related to its identity (e.g. label), quality, durability, reliability, safety or performance should be recorded in the investigational product complaint form provided and should be notified to Taewoong Medical Co., Ltd. If any adverse event is occurred in the subject due to device deficiency, the adverse event should be recorded in the case report form.

### **12.6. Expected Adverse Events and Precautions for Use**

#### **12.6.1. Expected Adverse Events**

< Expected Adverse Events during the procedures of the Niti-S SPAXUSTM Stent >

- Bleeding
- Stent misplacement
- Inadequate expansion
- Stent migration
- Pain
- Perforation

< Expected Adverse Events after Deployment of the Niti-S SPAXUSTM Stent >

- Bleeding
- Pain
- Perforation
- Stent misplacement
- Stent migration

- Stent occlusion
- Fever
- Pancreatitis
- Abscess formation
- Vomiting
- Pneumoperitoneum
- Intraperitoneal leakage
- Peritonitis
- Hematoma
- Inflammation
- Infection
- Fistula
- Ulceration
- Sepsis
- Rupture of intracystic artery
- Stent removal failure

#### **12.6.2. Precautions for Use of 'Niti-S SPAXUS™ Stent'**

##### **1) Contra-Indications**

- ① When the patient has hemodynamic instability
- ② When the patient has severe coagulopathy
- ③ Use for the reason other than the indications
- ④ Recapture during the deployment of the stent

##### **2) Precautions for Use**

- ① The instructions should be read carefully before using this device, and the device should be used and supervised by a trained physician. A careful understanding-in-depth of the techniques, principles, clinical applications and risks associated with the operation of the device is required prior to the procedure.
- ② Care should be taken for removal of the guidewire and the introducer system while the stent is not being fully deployed immediately after stenting.
- ③ Care should be taken for expanding the stent after deployment since it may cause perforation, bleeding and stent migration.
- ④ The device should be used after checking the expiration date specified in the package.
- ⑤ Fluoroscope is recommended otherwise the stent may be misplaced.
- ⑥ The expiration date should be checked, and the device should not be used if the expiration date has passed.

- ⑦ This medical device is supplied as sterilized and should not be used if the package is opened or damaged.
- ⑧ This medical device shall be used only once as single use devices, cannot be used by re-sterilizing.
- ⑨ If this device is used for vascular system, the safety and effectiveness of medical device cannot be guaranteed.
- ⑩ This device requires to take precautions for use, and should be used after fully considering the bleeding frequency, coagulopathy, radiation colitis, and proctitis of the patients.
- ⑪ In sensitive patients, allergic reaction may be caused by Nickel component of the stent.
- ⑫ The introducer should not be exposed to organic solvents such as alcohol.
- ⑬ The device should not be used together with Ethiodol or Lipiodol contrast agent.
- ⑭ Do not change the position of the stent after complete deployment.

## 13. CRITERIA FOR STUDY DISCONTINUATION AND DROP-OUT

The clinical study can be discontinued in accordance with the decision of the principal investigator, IRB or any regulatory agency. The subject can be discontinued the participation in the study or dropped out of the study due to the withdrawal of the consent or the safety issues.

### 13.1. Study Discontinuation

#### 13.1.1. Criteria for Discontinuation

- ① The investigator may discontinue the clinical study if it is judged that the continuation of the clinical study in the light of the results observed during the clinical study implementation affects the safety of the subject. The principal investigator should notify immediately about this matter to the sponsor, the IRB and the Ministry of Food and Drug Safety, and submit a detailed reason(s) for this action of the study suspension.
- ② The sponsor can make a decision to discontinue the clinical study for safety concerns or administrative reasons, and should notify the discontinuance to the principal investigator, IRB and the Ministry of Food and Drug Safety with submission of detailed reason(s) in writing for the discontinuance.

#### 13.1.2. Handling of Discontinuation

- ① If the clinical trial is discontinued, the principal investigator must notify all subjects within 30 days and collect all materials and items. In addition, the principal investigator should summarize the progress status and results of the clinical study and complete the case report

forms of all subjects as much as possible, and then, should return the investigational medical device to the sponsor.

- ② In the event of the early termination or discontinuation of the clinical study, the principal investigator should notify the study discontinuance in writing to the Ministry of Food and Drug Safety and IRB.

## 13.2. Study Drop-out

### 13.2.1. Criteria for Drop-out

- ① When a subject or legally acceptable representative requests to stop participating in the clinical study
- ② When a medical device is used or surgery and drug are used in combination which may affect the safety and effectiveness assessments
- ③ When an adverse event is occurred making the clinical study cannot be no longer carried out because it affects the safety of the subject.
- ④ When a subject fails to adhere to the details of the subject compliance presented in the informed consent including that the subject refuses to follow the instruction of the investigator, or fails to perform the treatment method adequately, which affect the effectiveness assessment.
- ⑤ Others such as when the principal investigator determines there is a problem in progressing the clinical study

### 13.2.2. Handling of Drop-out

- ① If a subject is dropped out of the study, the reason for drop-out and the clinical study-related records conducted before the drop-out will be recorded and retained.
- ② If a subject fails to visit the hospital during the clinical study, the reason should be made clear and the subject's condition should be checked.
- ③ Data of subjects who are dropped out will be included in the effectiveness and safety evaluation analysis unless there is a valid reason or reason.

## 14. Statistical Analysis

A two-tail test will be performed for statistics at a significance level of 0.05 unless otherwise specified, and the statistical analysis will be done using a statistical package SAS V9.4.

## 14.1. Assessment Analysis Set

The analysis of clinical success and the effectiveness endpoints will be conducted in FAS as the main analysis population, while the analysis of the safety evaluation variables will be conducted in the Safety Set.

► SS (Safety Set)

All subjects who attempted to receive the Niti-S SPAXUS™ Stent procedure among those who satisfied the inclusion/exclusion criteria and gave the informed consent for participation in this clinical study.

► FAS (Full Analysis Set)

Subjects who underwent the Niti-S SPAXUS™ Stent procedure and completed the primary effectiveness assessment among those who satisfied the inclusion • exclusion criteria and gave the informed consent for participation in this clinical study.

► PP (Per Protocol) Set

Subjects who have completed the study with no serious violation of the clinical investigation plan among those who satisfied the FAS.

Serious clinical investigation plan violations

- When a subject did not perform the treatment method properly
- When medical devices, surgery, or drugs that may affect the safety and effectiveness assessments for the investigational device, are used in combination

### 14.1.1. Effectiveness Assessment Analysis Set

The effectiveness assessment analysis is performed in FAS as the main analysis group. In other words, the analysis will be performed in the subjects who underwent the Niti-S SPAXUS™ stent and have the results of effectiveness assessment at the time point of the stent removal among those who satisfy the inclusion • exclusion criteria, consented to participate in the clinical study. However, analysis in the PP set will be also carried out and the results will be compared.

### 14.1.2. Safety Evaluation Analysis Set

The safety evaluation analysis is conducted in the Safety Set.

## 14.2. Statistical Analysis Method

### 14.2.1. Analysis of General Matters

In case of continuous variables with regard to the demographic and the clinical characteristics of the subjects, the descriptive statistics (number of cases, mean, standard deviation, median value, minimum and maximum values) are presented, whereas in case of categorical variables, the frequency and the percentage are presented. For the variances of continuous data, Paired t-test or Wilcoxon's signed rank sum test will be conducted whereas for the variations of categorical data, McNemar's test will be conducted.

### 14.2.2. Analysis of Effectiveness Assessment

#### 14.2.2.1. Analysis of Primary Effectiveness Assessment

The number and percentage of patients who achieved clinical success at the time of stent removal are presented. A one-sided 97.5% confidence interval is to be calculated to confirm the degree of non-inferiority for the reference value (96%) and the difference (Investigational device - reference value) and if the lower limit of the confidence interval is -10% or higher, the non-inferiority will be considered to be confirmed.

#### 14.2.2.2. Analysis of Secondary Effectiveness Assessment

Regarding the secondary effectiveness variables, for categorical data, the frequency and percentage as well as 95% confidence interval will be presented. For continuous data, descriptive statistics (number of cases, mean, standard deviation, median value, maximum and minimum values) are provided

- Technical success
- Stent lumen patency
- Stent removal success
- Procedure time

### 14.2.3. Analysis of Safety Evaluation

The safety evaluation variables such as the frequency and percentage of stent rupture, re-operation, reoperation, procedure or medical device related serious adverse events and deaths are presented, and a summary by each subject is described.

The descriptive statistics (number of cases, mean, standard deviation, median value, maximum and minimum values) are presented for the continuous variables such as all adverse events, vital

signs, and physical examinations collected from the subjects. The changes of post-stent application compared to pre-stent applications will be analyzed by using Paired t-test or Wilcoxon signed-rank test for continuous variables, and McNeamar's test for categorical variables. The adverse events are classified by using MedDRA and these cases are reported using 'Preferred term' and 'System organ class'. All adverse events are presented by the frequency (percentage) by subjects and the number of subjects. When calculating the subject frequency, if multiple cases of same adverse event occur in one subject based on 'Preferred term' and 'System organ class', it will be considered as one case. Whereas the severity and the causality differ for the same adverse event, it will be processed as the maximum severity and causality. The total number of subjects is used in calculating the subject percentage, and when calculating the number of cases, the case like the one mentioned above will be regarded as different adverse events.

For subjects experiencing the adverse event (or adverse device effect) at least one or more, the subject frequency and percentage will be presented and also a 95% confidence interval will be provided. In addition, for the serious adverse events and the subjects dropped-out of the study due to them, the frequency and percentage of subjects should be presented and listed.

#### **14.2.4. Statistical Processing of Missing Data**

For the effectiveness endpoints, no separate correction of missing data will be performed because the subjects whose effectiveness assessment is not performed are not to be included in the analysis according to the definition of the main analysis set. Also in the case of safety evaluation variables, the raw data shall be used as they are without any missing value correction.

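### Every effectiveness analysis leaves out subjects without a stent-removal-time result, Section 13.2.2 handles drop-outs differently, and no planned effectiveness table shows what the exclusion does to clinical or technical success

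*Combined protocol and SAP*

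**What the plan says.** Section 14.1 (repeated in the synopsis) defines three sets.

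- The Safety Set: "All subjects who attempted to receive the Niti-S SPAXUS™ Stent procedure", among eligible, consenting subjects. Sections 14.1 and 14.1.2 use it for safety only.
- The FAS: "Subjects who underwent the Niti-S SPAXUS™ Stent procedure and completed the primary effectiveness assessment", again among eligible, consenting subjects.
- The PP set: "Subjects who have completed the study with no serious violation of the clinical investigation plan among those who satisfied the FAS".

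On their use, Section 14.1 says: "The analysis of clinical success and the effectiveness endpoints will be conducted in FAS as the main analysis population". Section 14.1.1 restates the FAS as subjects with an effectiveness result at stent removal, and adds a PP analysis for comparison. Section 14.2.4 relies on this definition: no correction is made because "the subjects whose effectiveness assessment is not performed are not to be included in the analysis".

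Section 13.2.2 deals with drop-outs separately: "Data of subjects who are dropped out will be included in the effectiveness and safety evaluation analysis unless there is a valid reason". It gives no denominator, no scoring rule and no account of what a valid reason is. It does secure the information needed to explain losses: "the reason for drop-out and the clinical study-related records conducted before the drop-out will be recorded and retained", and "If a subject fails to visit the hospital during the clinical study, the reason should be made clear".

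Section 13.2.1 lists among the grounds for drop-out an adverse event that prevents continuation, and use of another device, surgery or drug that may affect the assessments. Technical success is assessed at Visit 2, the procedure day (Clinical Study Schedule and its note 13).

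**The concern.** In a single-arm study the primary result is one proportion against a fixed number, so who is in the denominator matters a great deal. Two of the drop-out grounds in Section 13.2.1 may reflect failure of the treatment. A subject who leaves on such a ground before the Day 30/60 CT is removed from the clinical success rate and is not counted as a non-success. The PP comparison cannot bring that subject back, because it only takes people out of the FAS.

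For technical success the outcome is known on the procedure day, yet the subject counts only if a result exists weeks later. A failed placement with no later CT would disappear from the very endpoint that is meant to record it. Whether it also fails the FAS on its other condition depends on whether 'underwent' covers a failed attempt. The Safety Set uses 'attempted', and the plan does not explain the difference.

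At stake is a pivotal non-inferiority conclusion that, with 31 to 35 subjects, can turn on one person.

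**Working it through.** **Inputs.** Section 9.2: reference 96%, assumed device rate 96%, margin 10 points, one-sided 2.5%, power 80%, withdrawal 10%. Section 14.2.2.1: one-sided 97.5% confidence interval, method not named. The lower limit for the success rate must therefore reach 96% − 10% = 86%. Because no method is named, Wald and exact (Clopper-Pearson) limits are both shown.

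**The plan's own figure.** n = (1.960 + 0.842)² × 0.96 × 0.04 / 0.10² = 30.14, rounded up to 31. Allowing for withdrawal, 31/0.9 = 34.4, rounded up to 35. Both match Section 9.2.

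**One excluded failure at the threshold.** The Wald lower limit is p − 1.96 × √(p(1 − p)/n). The exact limit is the 2.5% quantile of Beta(x, n − x + 1).

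| Method | Failure excluded | Failure counted |
|---|---|---|
| Wald | 30/31: 90.6%, pass | 30/32: 85.4%, fail |
| Exact | 34/34: 89.7%, pass | 34/35: 85.1%, fail |
| Wald, away from threshold | 31/31: 100%, pass | 31/32: 90.8%, pass |

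The number of failures that still reaches 86% is one (n = 31 to 33) or two (n = 34, 35) under Wald, and none under exact limits.

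**Does the exclusion favour the device?** That depends on who is lost. For illustration, assume 35 attempted procedures, true success of 86% among them, a fraction e excluded (5% or 10%, number excluded binomial), and a share s of the excluded who are failures. Success among those assessed is then (0.86 − e(1 − s))/(1 − e). The chance of passing, against the planned 2.5%, is:

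| Who is lost | Exact, e = 5% / 10% | Wald, e = 5% / 10% |
|---|---|---|
| Nobody (all 35 counted) | 0.5% | 11.5% |
| s = 14% (same failure rate) | 0.7% / 0.9% | 8.3% / 6.5% |
| s = 50% | 1.4% / 3.7% | 13.8% / 18.8% |
| s = 100% | 3.7% / 24% | 26% / 62% |

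The 11.5% Wald figure with nobody lost comes from the interval method and is not part of this point. With exact limits the chance exceeds 2.5% only once excluded failures reach about 4% of those attempted (0.90³⁵ = 0.025 and 0.90 − 0.86 = 0.04), that is 0.04 × 35 = 1.4 subjects.

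**Technical success.** Assume 3 of 35 placements fail and have no later result. On all attempted procedures the rate is 32/35 = 91.4%; in the FAS it is 32/32 = 100%.

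**How strict is a missing-as-non-success analysis?** For a device with 96% success among assessed subjects, the rate on all attempted is 0.96 × 0.95 = 91.2% at 5% loss and 0.96 × 0.90 = 86.4% at 10% loss. Of the trials that pass in the FAS, the share whose lower limit falls below 86% once missing results count as non-success is 46% to 81% (Wald) or 85% to 98% (exact) over that range of loss.

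**The case against.** Four points on the other side have weight.

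*The sections may not contradict each other.* A reader might infer that Section 13.2.2 flatly requires what Section 14 forbids. The text does not go that far. Section 13.2.2 has its exception, and a subject who leaves after the Day 30/60 CT but before Visit 6 is a drop-out who stays in the FAS, so both rules hold for that subject. What stands is that the exception is undefined, and that Section 13.2.2 says nothing usable about subjects lost before the CT.

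*The loss is not wholly invisible.* Section 14.2.3 reports re-operations, deaths, related serious adverse events and drop-outs due to serious events. A subject with a Day 60 CT who then receives a plastic stent remains in the FAS as a non-success (Section 11.1.2). Both are true, but nothing reported under Section 14.2.3 enters a success rate.

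*The examples rest on assumptions.* A failed placement need not lack a later result. In the AXIOS study described in Section 6.2, collections resolved in 27 of 29 stent recipients and in 30 of 33 overall; the difference of 3 equals the number given plastic stents, which suggests that they were followed. Technical success is also descriptive, with no test. This limits the size of the example. It does not justify filtering a procedure-day outcome by a later one.

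*The 96% reference was itself built largely on assessed subjects.* Of the 44 cases in the weighted average of Section 9.2, 29 come from the AXIOS study, where 33 were treated, 3 received plastic stents and 1 could not be evaluated. This stands. It argues against holding an all-attempted rate to the 86% bar, but not against showing that rate.

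**Conclusion.** The point holds as a gap in the planned analyses. Subjects without a stent-removal-time result leave every effectiveness analysis, outcome-related losses included, and no planned effectiveness table would show the effect. The drop-out wording in Section 13.2.2 needs reconciling with Section 14, and technical success is analysed on the wrong denominator for a procedure-day outcome.

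At the threshold one excluded failure changes the non-inferiority conclusion under either interval method; away from it nothing need change. The 91.4% against 100% for technical success rests on the assumption of three failed placements with no later CT.

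Two stronger readings are tempting and should be resisted. One is that the exclusion biases the result towards the device. Section 9.2 gives no reasons for the 10% withdrawal, so neither the direction nor the size is known; if those lost fail as often as the rest, the rate is unbiased. The other is that an FAS pass should be called not robust when it fails with all missing results counted as non-success. That would hold the trial to a bar built largely on assessed subjects, and one that a device with 96% success among assessed subjects would often miss: in roughly half of its FAS passes at the mildest setting examined, and in most of them at the others.

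This should be fixed before the results are known, because a rule for missing results chosen afterwards would be open to the charge of following the data.

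**What to change.** 1. Analyse technical success on all subjects in whom the procedure was attempted. The Safety Set already is that group.
2. Keep the FAS clinical success result as primary. Prespecify beside it one supporting analysis of all attempted subjects, with every missing Day 30/60 result counted as a non-success. Label it a lower bound, and print with it the number of missing results and the reasons, taken from the Section 13.2.2 record. Attach no pass/fail or robustness rule to it, and do not rescore CT results that exist.
3. Reconcile Section 13.2.2 with Sections 14.1, 14.1.1 and 14.2.4 (and the synopsis): say what a valid reason is, how a subject lost before the CT is treated, and whether a failed placement counts as having undergone the procedure.

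The cost is one extra table, a supporting figure less favourable than the FAS rate, and amended text with IRB approval and, as necessary, Ministry approval (Section 16.3). The endpoint, primary set, reference, margin and subject number stay as they are, so the power of the primary analysis is unchanged.
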